2. Examine the preliminary effects of the MOMP intervention on measures of maternal psychobehavioral factors (i.e., depressive symptoms, anxiety, ruminations, PA self-efficacy, attachment) at baseline, midpoint and end of the 12-week intervention, and at 6-weeks postpartum and at 10-20 months postpartum, and on baby♦'s birth weight, compared with archival data from depressed women receiving the UC, to estimate effect sizes to inform future studies.
3. Identify DNA methylation (DNAm) patterns associated with chronic depressive symptoms during pregnancy and investigate whether participation in the MOMP intervention targets these patterns: This aim will be accomplished by evaluating both genome-wide and gene-specific DNAm patterns (e.g., candidate genes putatively related to depression, pregnancy, and mindful interventions: Nr3c1, NGFI-A, FKBP5, BDNF, TrkB, HP1BP3, TTC9B). These patterns will be compared with patterns in recently collected archival data from pregnant women with and without depressive symptoms receiving UC.

3. * Describe the study's background and significance, including citations, or upload a citation list in document upload. Use lay language whenever possible.

Chronic and recurrent depressive symptoms are a significant public health problem.¹ Women with chronic depressive symptoms face significant treatment challenges during pregnancy. Close to 20% of women experience clinically significant depressive symptoms during pregnancy (e.g., feelings of sadness, anhedonia, sleep alterations, and fatigue, among others),² with the majority manifesting a recurrence of symptoms rather than a new onset.³⁻⁵ Although there are numerous pharmacological treatments available for depressive symptoms, data are conflicting with respect to safety of antidepressant medications during pregnancy and there is little research addressing efficacy of non-pharmacological therapies in this population.^{3,6,7} Currently, no therapies are universally effective at decreasing depressive symptoms and uniformly accepted as low obstetrical and fetal risk.^{8,9} Further, many pregnant women are concerned about stigma, side effects, fetal effects, and/or costs of the ♦usual care♦ (UC: antidepressants, psychotherapy) for symptoms and elect to avoid or decrease UC during pregnancy.¹⁰⁻¹⁶ Hence, many women with depressive symptoms remain un- or under-treated.³

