Weekly contact by study staff (phone or email per participants' choice): Study staff will maintain regular contacts in the mode of participants' choice during the 12 weeks of the intervention. This is intended to help with retention as well as monitoring for adverse events. Study staff will collect data about minutes of physical activity during these weekly phone contacts. No survey or other data will be collected during this contacts, unless a participant verbalizes a physical or psychological adverse event.

Study Visit #7 (Intervention Week 6): Participants will be asked to complete questionnaires at the midpoint of the 12-week intervention at home electronically (if they have computer access at home) or in paper/pencil form (for those without sufficient comfort levels or access to a computer~~to~~RA will pick them up at participants~~to~~ next class).

Study Visit #14-- Last visit during pregnancy: Participants will complete another set of questionnaires electronically or in paper/pencil format. A blood sample will also be collected (8 ml blood by venipuncture in 2 EDTA [purple top] tubes).

Study Visit #15-- Postpartum Visit/Interview Session: Each participant will meet with study staff (RA, PD, and/or PI) to complete the questionnaires and participate in a semi-structured interview. Specific questions for this semi-structured interview are found in the Study Interview Guides/Scripts document. This interview will be audiotaped (and later transcribed).

Note: if a participant chooses to withdraw from the study, they will be given the opportunity to give their reasonings for withdrawal in the form of a short interview with research staff.

**** For Addendum Feb 2018: "Long-Term Follow-Up" study visit:** participants who "opted-in" to being contacted for future study will be contacted via email and/or phone about answering survey questions. Participants will give consent via REDCap (or in rare instances, may choose paper & pencil, which will be completed in-person with the research nurse) and will answer survey questions, using the same measures that have been used at previous study visits.

STUDY MEASURES

** SEE TABLE 1. STUDY MEASURES BY TIMEPOINTS

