(a) **Depressive symptom severity:** Depressive symptom severity will be evaluated using the Patient Health Questionnaire (PHQ-9), a widely used instrument which has been validated during pregnancy.¹⁶⁹ The PHQ-9 includes self-report items regarding depressive symptoms over the past two weeks. Total scores range from 0-27: 0-4 indicates minimal depression, 5-9 mild depressive symptoms, 10-14 moderate depressive symptoms, 15-19 moderately severe depressive symptoms, and =20 severe depressive symptoms. For analysis purposes, presence of depressive symptoms will be defined as a score =10 on the PHQ9. The PHQ-9 includes a question on suicidal ideation,^{202,203} which will be used for monitoring for adverse events as described in the Protection of Human Subjects section. Because the archival comparison group database includes the Edinburgh Postnatal Depression Scale (EPDS)¹⁸⁰ in the pregnancy and postpartum assessment, we will also administer this survey at the same timepoints. The EPDS is a widely used and validated measure of depressive symptoms, with 10 questions appropriate for the prenatal and postpartum woman; a score =10 (range 0-30) suggests possible depressive symptoms. Guidelines regarding management of participants with depressive symptoms or suicidal thoughts are detailed in the Protection of Human Subjects section but in brief, the researchers will be poised to assess further and make referrals to appropriate community organizations, healthcare providers, or emergency departments in cases of psychological distress (score =20 on PHQ9 and/or suicidal ideation) or physical injury. (b) **Stress:** The Perceived Stress Scale-10 (PSS-10), a widely used, psychometrically sound instrument, will assess the degree to which a participant perceives stress in her life during the past month.¹⁸¹⁻¹⁸⁵ The PSS-10 asks respondents to report about feelings such as unpredictability, uncontrollability, and overloading of stress in their lives; scores range from 0-40; higher scores correspond to a higher perceived stress level.¹⁸⁴ (c) **Anxiety:** Current levels of anxiety (state anxiety) will be evaluated with the State-Trait Anxiety Inventory, Form Y (STA). This study focuses specifically on state anxiety, as this score is sensitive to women's anxiety during pregnancy and is more likely to demonstrate change within an intervention period.^{190,204} This measure yields reliable and valid scores.¹⁸⁷⁻¹⁸⁹ The STA scores range from 20-40, with higher scores representing higher levels of state anxiety. (d) **Rumination:** Rumination, or repetitive self-critical thinking, will be evaluated with the 10-item Ruminative Responses Scale (RRS) which assesses the propensity to ruminate in association with sadness or depression. A psychometrically sound and widely used instrument, the RRS asks respondents to rate how often they experience various aspects of rumination.¹⁹³ The RRS has two factors of brooding (self-critical pondering) and reflecting (emotionally-neutral pondering or brainstorming). (e) **Self-Efficacy for Physical Activity:** The Physical Activity Self-Efficacy Scale (PASES)^{194,195} is an eight question scale which contains items about SM of physical activities and social support regarding PA. This psychometrically sound scale was selected because of its specific focus on SM of PA. Originally designed for adolescents, the wording has been slightly adapted for an adult sample. (f) **Maternal-Fetal/Child Attachment:** The Maternal-Fetal Attachment Scale (MFAS)^{32,198} assesses the extent to which women have an affiliation and interaction with their unborn child (during pregnancy) and their infant (during PP). Maternal depression has a proximal effect on maternal-child attachment,¹⁷ hence it is highly relevant to evaluate attachment in relation to an intervention designed to address depression.

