Aim 2: Examine the potential effects of the MOMS intervention on measures of maternal psychological symptoms assessed at multiple time points (Table 1) and on the baby²⁰⁶s birth weight, with the primary variable of interest, depressive symptoms, measured by the PHQ-9. Means, variances and covariances/ correlations along with 95% confidence intervals for each of the three groups (intervention [MOMS], comparison group with depressive symptoms [positive], and comparison group without depressive symptoms [negative]) will be calculated for each of the four study time points (baseline [BL], IW6, IW12, postpartum [PP]). A mixed linear model (MLM) will be fit to the data. The model will include one between-subjects effect (Group: MOMS, positive comparison, negative comparison), one within-subject effect (Time: BL, IW6, IW12, PP), and the interaction between group and time. This model will allow estimation of changes from baseline in levels of psychological symptoms within and between groups at each time point. Possible covariates, such as the initiation of UC (medications, psychotherapy), will be fully explored during analysis. Data from participants who drop out of the intervention will be retained in the analytical portion of the study according to intent-to-treat principles. Correlations will be calculated between baby²⁰⁶s birth weight and group (intervention, positive comparison, negative comparison). Figure 2 summarizes data collection timepoints for the study in relation to the archival comparison group database.

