Internet Data Collection Details

1. * Check all that apply:

Passive Data Collection

 Active Data Collection

2. If participants could be minors, describe how parents or LARs will be notified of the research:

ID: MS8_HM20006941

[View: SF - Active Data Collection](#)

Active Data Collection

1. * Describe the technology chosen for collecting the data and transmitting data securely over the internet. Give the rationale for selecting this technology:

REDCap is a VCU-approved, secured system for collecting self-reported data from participants. Learn more about REDCap here: <http://www.ts.vcu.edu/software/2530.html>. Participants will enter their data on REDCap.

2. * **Describe how data will be linked or unlinked to identifiers including email addresses, names, and/or IP address.**
Data will only be linked to study IDs.

3. * **Is there an alternative method for completion of the data collection other than the internet:**

Yes
 No

4. **If yes, describe the alternative(s):**

Participants will also have the option to complete paper/pencil surveys if they are not comfortable using the computer.

5. * **Describe how individuals will be able to skip or not answer particular questions. If any questions are mandatory, provide justification:**

As with a paper/pencil survey, participants will be able to skip or not answer questions on the REDCap survey. If a participant decides at any point during the data collection to withdraw their data or to start over, they may select an option at the end of the survey to "discard all data".

6. **If not including children, describe any procedures used to verify that research participants are adults:**

We will have already confirmed participants' ages during the initial study visit

ID: MS8_HM20006941

View: SF - Data Confidentiality and Storage

Data Confidentiality and Storage

 Confidentiality refers to the way private, identifiable information about a participant or defined community is maintained and shared.

1. * **Specify where this study's paper and electronic research data and/or physical specimens will be stored and how they will be secured from improper use and disclosure:**

See the help text for additional guidance.

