- 5. * Is it likely investigators could discover a participant's previously unknown condition (eg disease, suicidal thoughts, wrong paternity) or if a participant is engaging in illegal activities:**

Yes
 No

- 6. If yes, explain how and when such a discovery will be handled:**

During screening: if an individual contacts study staff and is ineligible for the study but has a concerning psychological risk (e.g. high score on the PHQ9 (or endorses suicidality) or signs of psychosis or mania), she will be provided with phone numbers to the crisis/emergency response teams of local mental health agencies (Henrico County Community Services Board: [contact]; Chesterfield County Community Services Board: [contact]; Richmond Behavioral Health Authority: [contact]) and/or will be directed for emergent care at the local emergency department.

For participants: It is possible that some participants will experience increased intrapersonal or interpersonal psychological distress as a result of participating in assessment or intervention. In the vast majority of cases, we believe that any increased distress experienced will be mild and transitory in nature.

IF Significant worsening of depressive symptoms= participant scores ≥ 20 on the PHQ9 (with no endorsement of suicidality) --> PI will contact participant and conduct the MINI suicide module as soon as information is obtained. If suicide risk is low ($=8$), applicant will ask participant to be in touch with her healthcare provider. Contact information for local resources will be provided, as needed (e.g. Henrico County Community Services Board: [contact]; Chesterfield County Community Services Board: [contact]; Richmond Behavioral Health Authority: [contact]; local emergency departments).

IF endorsement of suicidality item on PHQ9 or verbal report of suicidality --> PI will contact participant and conduct the MINI suicide module as soon as information is obtained. If suicide risk is high ($=9$), PI will ensure participant is accompanied by a family member or friend to their healthcare provider or local emergency department for immediate evaluation. PI will contact study team and clinical psychologist Co-I ([name]) and/or psychiatrist-collaborator ([name]) to assess the concern (within 1 day).

See also page 8 on the DSMP.

- 7. * Describe any potential risks or harms to a community or a specific population based on study findings:**
n/a

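### As worded, the PI-contact rule treats a skipped PHQ-9 suicide item like a 'no' when the total is below 20; exposure is greatest at the mainly online 10-20 month survey

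*Combined protocol and SAP*

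**What the plan says.** **Skipping.** The form at Active Data Collection, item 5, asks which questions are mandatory and why. The answer is that "participants will be able to skip or not answer questions on the REDCap survey". No exception is made for the suicide item.

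**Safety role of the item.** Under Maternal Psychological Measures (a), the plan says of the PHQ-9 suicidal-ideation question: "which will be used for monitoring for adverse events".

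**Triggers.** Risks, Discomforts, Potential Harms and Benefits, item 6, sets out two routes to PI contact and the MINI suicide module. The first is a PHQ-9 of 20 or more "with no endorsement of suicidality". The second begins "IF endorsement of suicidality item on PHQ9 or verbal report of suicidality". The answer closes with "See also page 8 on the DSMP". It does not mention an unanswered item.

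**A broader commitment.** Social/Behavioral Project Details, item 3, and section 1.3.3 of the Risks section say that the team will assess further and refer if it detects suicidality or a large rise in depressive symptoms. Neither place defines 'large' or mentions blanks.

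**Staff contact.** Weekly contacts, with a question about physical or psychological concerns, run through the 12 intervention weeks. The 6-week postpartum questionnaires are completed at a meeting with staff. The long-term follow-up, marked "For Addendum Feb 2018", approaches women by email or phone. It is then done in REDCap, with in-person paper forms only rarely.

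**Content of the late survey.** Aim 2 lists psychobehavioral assessments, depressive symptoms among them, "at 6-weeks postpartum and at 10-20 months postpartum". The long-term follow-up paragraph says that the survey reuses the instruments of earlier visits.

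**The concern.** A blank is neither an endorsement nor a denial. A rule that acts only on an endorsement, a spoken report or a high total cannot tell a woman who declined the question from one who answered 'no'. The women entered with a PHQ-9 of at least 10 and, by inclusion criterion 6, without suicidal ideation. New ideation is therefore what later monitoring has to pick up.

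During the intervention and at 6 weeks postpartum, staff contact gives a second chance for a verbal report. At 10-20 months no comparable safety contact is described, so the questionnaire carries most of the monitoring. At stake is participant safety; no estimate or trial conclusion is affected.

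**Working it through.** There is no sample-size or error-rate figure to reproduce. The check enumerates the item 6 rule and then sizes the affected group.

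**Rule.** Let S be the sum of the other eight PHQ-9 items. Assume each item is scored 0-3 (27 / 9 = 3), so S runs from 0 to 8 × 3 = 24. Contact follows if the total is 20 or more, or if the suicide item is above 0. Verbal report is set aside, since it does not depend on the form. The plan gives no scoring rule for a missing item, so two assumptions are tried.

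| Suicide item | Total used | Contact when |
|---|---|---|
| 1, 2 or 3 | S + item | every S from 0 to 24 |
| 0 ('no') | S | S of 20-24 |
| blank, left out of the total | S | S of 20-24 |
| blank, prorated | S × 9/8 | S of 18-24 |

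- With blanks left out, the action for a blank equals the action for a 'no' at all 25 values of S. For S of 0-19, neither prompts contact.
- With proration, S = 17 gives 17 × 9/8 = 19.13 and S = 18 gives 20.25. A blank then differs from a 'no' only at S of 18 and 19. For S of 0-17 it is still handled like a 'no'.
- With blanks left out, the score trigger can be lost as well. If the true answer would have been 3 with S = 17, 2 or 3 with S = 18, or 1 to 3 with S = 19, the full total reaches 20 but the recorded total does not.

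**Number of women.** The inclusion criteria give 41. The sample-size justification cites 20-40% attrition in earlier studies: 41 × 0.6 = 24.6 and 41 × 0.8 = 32.8, so about 25-33. The skip rate is not in the documents; 1-5% is assumed.

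- One survey: 24.6 × 0.01 = 0.25 to 32.8 × 0.05 = 1.64 blanks; with all 41 answering, 41 × 0.05 = 2.05.
- Five time points (baseline, week 6, week 12, 6 weeks postpartum, 10-20 months): 5 × 24.6 × 0.01 = 1.2 to 5 × 41 × 0.05 = 10.3 blanks.

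Follow-up is limited to women who agreed to be contacted again, so 25-33 may be high for the late survey.

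**Dates.** The Documents list shows the data safety monitoring plan (DSMP) and the adverse-event protocol as revisions of 9-7-16. The follow-up consent forms, the script and the revised measures table carry 4-3-18. From 7 September 2016 to 3 April 2018 is 573 days, about 19 months. The listed safety files were therefore not revised for this survey.

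**The case against.** The strongest objection is that the deciding documents are not in view. Item 6 answers a form question about handling a discovery, which a blank is not, and it refers the reader to the DSMP. The DSMP, adverse-event protocol, manual of operations, follow-up script and follow-up consent forms were not available, and any of them may hold a rule for blanks. A rule written for every PHQ-9 would cover the late survey without revision. This stands, and it is why the request is to add the step or cite it.

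Three stronger readings are tempting, and the documents do not support them.

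- *No woman scoring 15-19 with a blank would be contacted.* The commitment to assess further after a large rise in symptoms could prompt contact below 20. The enumeration describes item 6 only.
- *The 2016 file dates show that the survey is uncovered.* They show only that those versions predate it.
- *The statement that follow-up needs no new training reveals a safety gap.* The same training section covers processes for elevated depression scores, and the statement introduces the follow-up contact person. It reads as a staffing note.

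PHQ-9 use at 10-20 months is also inferred. The reuse of earlier instruments is the main support. The Aim 2 analysis plan works "with the primary variable of interest, depressive symptoms, measured by the PHQ-9", but its model lists only four time points, ending postpartum. The revised measures table would settle this and was not available.

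Finally, skipping is a deliberate choice, and calling a woman because she declined a sensitive item is a trade-off on which ethics boards may differ. That supports keeping the item optional and limiting the response to one contact.

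**Conclusion.** The point holds for the wording of item 6: a blank suicide item with a total below 20 prompts the same response as a 'no'. That is the effect of silence, not an instruction to staff. A verbal report still triggers action at any time, and a blank with the other eight items at 20 or more still leads to the MINI suicide module.

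Exposure is greatest at the 10-20 month survey. The email or phone approach and the named contact person give some opening for a verbal report, but neither is described as a safety check. The expected number is about 0-2 women at that survey. This rests on the assumed skip rate and on the inference that the PHQ-9 is included; women with undisclosed ideation would be at most that number.

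This is a minor point, worth acting on because the consequence for one woman could be serious and the remedy is cheap. Confidence is medium because of the unseen safety documents.

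**What to change.** Add one sentence to Risks, item 6: a blank or declined PHQ-9 suicide item at the 10-20 month survey leads to one contact by the PI. The team may extend this to earlier time points, which are already partly covered by the weekly contacts and the staffed visit. Keep the item skippable and leave the option to discard all data as it is.

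If the DSMP, adverse-event protocol or April 2018 follow-up script already contains the step, cite it in item 6 and confirm that it applies to this survey.

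The cost is one amended sentence plus, on the assumed 1-5% skip rate, about 0-2 extra PI contacts at the late survey, or about 1-10 if applied at all five time points. Some women may find the call unwelcome, and a woman may still decline to answer.
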